7. SAMPLE SIZE JUSTIFICATION

A maximum of 36 participants will be enrolled to study intervention with the intention that at least 6 participants randomized to LY3819253 have sufficient evaluable data in each cohort.

This would mean at least 12 participants with evaluable data if Cohorts 1 and 2 only are enrolled, or 18 participants if the optional Cohort 3 is also enrolled.

The sample size is not powered on the basis of statistical hypothesis testing. However, based on an assumption of 40% coefficient of variation (CV) for between subject variability in a PK parameter of interest, 6 subjects on active treatment per cohort may provide approximately 70% chance to ensure that a PK parameter's 90% confidence interval (CI) falls within (0.7, 1.43) over the corresponding geometric mean, such as AUC(0-∞).

A participant will be considered evaluable when the participant completes up to 29 days of study procedures. When a participant does not complete up to 29 days of study procedures, the sponsor will be consulted if the participant will need to be replaced.

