9.3.2 Pharmacokinetic Statistical Methodology

All tests of treatment effects will be conducted at a 2-sided alpha level of 0.1, unless otherwise stated, and all CIs will be given at a 2-sided 90% level.

The primary parameters for analysis will be AUC(0- ∞) of LY3819253 following SC administration. Other noncompartmental parameters, such as half-life, t_{max} , apparent clearance, and volume of distribution following SC administration may be reported.

The natural log (ln)-transformed AUC(0- ∞) will be analyzed using an analysis of variance model. The model will include dose as a factor. Body weight may be tested as a covariate and kept if needed.

The least squares mean for each treatment, difference in least square means between the treatments, and corresponding 90% CI will be calculated; these values will then be back-transformed to give the geometric least square mean, ratio of geometric least square means, and corresponding 90% CI.

Example SAS code for the analysis:

```
proc mixed data=pk;
  class dose;
  model log_pk = dose / alpha=0.1 cl residual ddfm=kr2;
  lsmeans dose / cl pdiff;
  ods output lsmeans=lsm;
  ods output diffs=diff;
  ods output tests3=tests;
run;
```

In addition to noncompartmental analysis, the data may be combined with data from other studies to be analyzed using non-linear mixed-effect modelling of the PK data. This analysis will be the responsibility of Eli Lilly PK/PD group.

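### The approximately 70% precision figure in SAP 7 fits a 90% CI built on one cohort's own variance; the pooled-variance CIs planned in SAP 9.3.2 have about an 89% chance for a dose mean and about 35% for the 700 mg/350 mg ratio

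*SAP*

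**What the plan says.** SAP 7 gives one quantitative argument for the sample size. It is "based on an assumption of 40% coefficient of variation (CV) for between subject variability in a PK parameter of interest", and it concludes that "6 subjects on active treatment per cohort may provide approximately 70% chance" of a 90% CI lying inside (0.7, 1.43) relative to the geometric mean, with AUC(0-∞) as the example. Protocol 9.2 makes the same statement. Neither document gives the formula, the variance estimator or the degrees of freedom. SAP 7 counts a minimum of 12 evaluable participants from the first two cohorts, and 18 when Cohort 3 is added.

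SAP 9.3.2 specifies the AUC(0-∞) analysis as an ANOVA on the log scale: "The model will include dose as a factor". The intervals are of two kinds: "The least squares mean for each treatment, difference in least square means between the treatments, and corresponding 90% CI will be calculated". They are then back-transformed to geometric means and ratios, and "all CIs will be given at a 2-sided 90% level". The example code has the model line "model log_pk = dose / alpha=0.1 cl residual ddfm=kr2" and no REPEATED, RANDOM or GROUP specification, so one residual variance is shared by all dose levels. SAP 9.1 lists descriptive statistics, including the geometric mean and geometric CV, but no separate per-cohort CI.

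**The concern.** A sample size statement should describe the analysis that will be run. This one appears to rest on a variance estimated from six people, whereas the planned model estimates it from at least twelve. Pooling raises the degrees of freedom, so the dose-mean intervals should do better than stated. The ratio interval has twice the variance of a dose-mean interval and should do clearly worse, and no precision is given for it anywhere. At stake is what readers expect of the results: how tightly each dose's exposure will be known, and how little two cohorts of six can say about the ratio of exposures between doses.

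**Working it through.** **Inputs**
- CV 40% (SAP 7). Log-scale SD σ = √ln(1 + 0.4²) = 0.3853. The common shortcut σ = 0.40 is run alongside.
- Limit on the log half-width: L = ln(1/0.7) = 0.3567. Using ln 1.43 = 0.3577 moves each result by less than half a percentage point.
- Two-sided 90% CI (SAP 9.3.2).
- n = 6 evaluable on active per cohort, Cohorts 1 and 2 (SAP 7).
- Degrees of freedom: 6 − 1 = 5 for a cohort's own variance; 12 − 2 = 10 for the pooled model without a covariate.

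**Formula.** The half-width is t(0.95, df) · s · √(m/n), with m = 1 for a mean and m = 2 for a ratio of two equal groups. Since df·s²/σ² follows a chi-square distribution,

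P(half-width ≤ L) = P(χ²_df ≤ df · [L / (t · √(m/n) · σ)]²).

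**Step 1: reproduce the plan's figure.** Own variance, 5 df, t = 2.015, √(1/6) = 0.4082. The largest acceptable SD is 0.3567/(2.015 × 0.4082) = 0.4336. Then 5 × (0.4336/0.3853)² = 6.33 and P = 72.5%. With σ = 0.40 it is 68.1%. The two bracket the stated 70%.

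Other readings tried at n = 6 do not fit. Pooled degrees of freedom give 85% to 95% for a mean. Requiring the interval to lie within the limits around the true mean gives 33% with 5 df and 38% with 10 df.

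**Step 2: planned dose mean.** 10 df, t = 1.812. The largest acceptable SD is 0.3567/(1.812 × 0.4082) = 0.482. Then 10 × (0.482/0.3853)² = 15.7 and P = 89.0%.

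**Step 3: planned ratio.** √(2/6) = 0.5774. The largest acceptable SD is 0.3567/(1.812 × 0.5774) = 0.341. Then 10 × (0.341/0.3853)² = 7.83 and P = 35.4%. When s equals σ, the interval factor is exp(1.812 × 0.3853 × 0.5774) = exp(0.403) = 1.50, which is wider than 1.43.

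| 90% CI, 6 per cohort, Cohorts 1 and 2 | df | σ = 0.385 | σ = 0.40 |
|---|---|---|---|
| One cohort, own variance | 5 | 72.5% | 68.1% |
| Dose mean, planned model | 10 | 89.0% | 85.0% |
| 700 mg/350 mg ratio, planned model | 10 | 35.4% | 29.9% |

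**Sensitivity (σ = 0.385 unless stated)**
- Body weight kept as a covariate, costing 1 df and ignoring any variance reduction: 86.9% for a mean, 35.1% for the ratio.
- All 7 planned active participants evaluable in each of two cohorts (12 df): 96.9% and 49.9%.
- Three cohorts of 6 as separate model levels (15 df): 95.1% and 36.3%.
- Cohort 3 with 5 evaluable, separate levels (14 df): 94% for a mean in Cohorts 1 and 2, 85% in Cohort 3, and 28% for a ratio involving Cohort 3.
- Cohorts 2 and 3 merged as one 700 mg level (6 against 12, 16 df): 350 mg/700 mg ratio 68%, or 59% with σ = 0.40.

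**The case against.** The strongest reply is that nothing has been miscalculated. The 70% is reproducible, it is hedged as approximate, and both documents say that the study is not powered for hypothesis tests. The statement is made per cohort and for PK parameters in general. Cohorts are enrolled in sequence after safety reviews, doses may be adjusted, and Cohort 3 is optional. A figure based on one cohort's variance holds however many cohorts are enrolled, and it errs on the safe side for the dose means. All of this stands.

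A reader might go further in three ways that the documents do not support.
- One might call the 70% an arithmetic error. It is correct for the interval it appears to describe; the mismatch is with the interval planned elsewhere in the SAP.
- One might say that the plan overstates the precision of the ratio twofold. SAP 7 sets its limits relative to a geometric mean and never claims 70% for a ratio.
- One might fault Protocol 9.2 as well. Protocol 9.4.2 specifies noncompartmental analysis and no pooled ANOVA, so the mismatch arises only inside the SAP.

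The reply does not remove the narrower point: SAP 7 is the precision statement for an analysis that SAP 9.3.2 defines differently, and the reader is not told so.

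**Conclusion.** The point holds as a mismatch between SAP 7 and SAP 9.3.2, and it is minor. With two cohorts of 6, the stated 70% is about 15 to 19 percentage points below the chance for the planned dose-mean interval, so it is conservative there. It is about twice the chance for the planned ratio interval, to which it should not be applied. The sample size is not shown to be inadequate.

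The conclusion rests on these assumptions:
- That the 70% comes from a single cohort's variance is inferred from reproducing it, because no formula is given.
- The limits are read as multiples of the estimated geometric mean.
- The model is as in the example code, with no body-weight covariate.
- Exactly 6 participants per cohort are evaluable.

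The two-cohort figures do not depend on how Cohort 3 is handled. Three-cohort figures do. Protocol 4.1.1 lets Cohort 3 close once 5 participants are randomized to active and sets no evaluable minimum there. The code classifies by dose, under which the two 700 mg cohorts could merge, although the treatment list in SAP 6 keeps them apart.

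**What to change.** Change SAP 7 only. Have the sponsor confirm the basis of the 70%, state that it refers to a CI using a single cohort's own variance, and add the figures for the planned model, for example:

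> Under the pooled-variance ANOVA in Section 9.3.2, without a body-weight covariate and with Cohorts 1 and 2 only, 6 evaluable participants per cohort give about an 89% chance that the 90% CI of a dose's geometric least squares mean lies within (0.70, 1.43) of the estimate, and about a 35% chance for the ratio of the two treatments (log SD 0.385).

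Leave out three-cohort figures, or state that they assume 6 evaluable participants in Cohort 3 and Cohorts 2 and 3 as separate model levels. Protocol 9.2, enrolment and the analysis stay as they are. The cost is a short addition to one SAP section; the downside is that the low precision of the ratio becomes visible.

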8. DEFINITION OF ANALYSIS POPULATIONS

The "Safety" population will consist of all participants who were randomly assigned and who received study intervention (LY3819253 or placebo). Participants will be analyzed according to the intervention they actually received.

The "Pharmacokinetic" population will consist of all treated participants who received study intervention (LY3819253) and have sufficient evaluable PK samples.

All protocol deviations that occur during the study will be considered for their severity/impact and will be taken into consideration when subjects are assigned to analysis populations.

9. STATISTICAL METHODOLOGY

9.1 General

Data listings will be provided for all data that is databased. Summary statistics and statistical analysis will only be presented for data where detailed in this SAP. For continuous data, summary statistics will include the arithmetic mean, arithmetic standard deviation (SD), median, minimum, maximum and N; for log-normal data (e.g. the PK parameters: area under the concentration versus time curve [AUCs] and maximum observed drug concentration [C_{max}]) the geometric mean and geometric CV will also be presented. For categorical data, frequency count and percentages will be presented. Data listings will be provided for all subjects up to the point of withdrawal, with any subjects excluded from the relevant population highlighted. Summary

statistics and statistical analyses will generally only be performed for subjects included in the relevant analysis population. For the calculation of summary statistics and statistical analysis, unrounded data will be used.

Mean change from baseline is the mean of all individual subjects' change from baseline values. Each individual change from baseline will be calculated by subtracting the individual subject's baseline value from the value at the timepoint. The individual subject's change from baseline values will be used to calculate the mean change from baseline using a SAS procedure such as Proc Univariate.

Data analysis will be performed using SAS[®] Version 9.4 or greater.

9.2 Demographics and Subject Disposition

Subject disposition will be listed. The demographic variables age, sex, race, ethnicity, body weight, height and body mass index will be summarized and listed. All other demographic variables will be listed only.

9.3 Pharmacokinetic Assessment

9.3.1 Pharmacokinetic Analysis

Noncompartmental methods applied with a validated software program, Phoenix WinNonlin (Certara, Version 8.1 or later) to the serum concentrations of LY3819253 will be used to determine the following PK parameters, when possible:

Parameter	Units	Definition
AUC(0-∞)	µg*h/mL	area under the concentration versus time curve from time zero to infinity
%AUC(t _{last} -∞)	%	percentage of AUC(0-∞) extrapolated
AUC(0-t _{last})	µg*h/mL	area under the concentration versus time curve from time zero to time t, where t is the last time point with a measurable concentration
C _{max} ^a	µg/mL	maximum observed drug concentration
t _{max}	h	time of maximum observed drug concentration
t _{1/2}	h	half-life associated with the terminal rate constant (λ _z) in non-compartmental analysis
CL/F	L/h	apparent total body clearance of drug calculated after extra-vascular administration
V _Z /F	L	apparent volume of distribution during the terminal phase after extra-vascular administration

^a Serum LY3819253 drug concentration units will come in from the bioanalytical lab as ng/mL to one decimal place; the data will be transformed (unrounded) to µg/mL for analysis and reporting.

Additional PK parameters may be calculated, as appropriate. The software and version used for the final analyses will be specified in the CSR. Any exceptions or special handling of data will be clearly documented within the final study report.

Formatting of tables, figures and abbreviations will follow the Eli Lilly Global PK/PD/TS Tool: NON-COMPARTMENTAL PHARMACOKINETIC STYLE GUIDE. The version of the tool effective at the time of PK analysis will be followed.

General PK Parameter Rules

- Actual sampling times will be used in the final analyses of individual PK parameters, except for non-bolus pre-dose sampling times which will be set to zero.
- C_{max} and t_{max} will be reported from observed values. If C_{max} occurs at more than one timepoint, t_{max} will be assigned to the first occurrence of C_{max}.
- AUC parameters will be calculated using a combination of the linear and logarithmic trapezoidal methods (linear-log trapezoidal rule). The linear trapezoidal method will be applied up to t_{max} and then the logarithmic trapezoidal method will be used after t_{max}. The minimum requirement for the calculation of AUC will be the inclusion of at least three consecutive serum concentrations above the lower limit of quantification, with at least one of these concentrations following C_{max}. AUC(0-∞) values where the percentage of the total area extrapolated is more than 20% will be flagged. Any AUC(0-∞) value excluded from summary statistics will be noted in the footnote of the summary table.
- Half-life associated with the terminal rate constant (λ_z) in non-compartmental analysis (t_{1/2}) will be calculated, when appropriate, based on the apparent terminal log-linear

portion of the concentration-time curve. The start of the terminal elimination phase for each subject will be defined by visual inspection and generally will be the first point at which there is no systematic deviation from the log-linear decline in serum concentrations. Half-life will only be calculated when a reliable estimate for this parameter can be obtained comprising of at least 3 data points. If $t_{1/2}$ is estimated over a time window of less than 2 half-lives, the values will be flagged in the data listings. Any $t_{1/2}$ value excluded from summary statistics will be documented in the footnote of the summary table.

- A uniform weighting scheme will be used in the regression analysis of the terminal log-linear portion of the concentration-time curve.
- The parameters based on predicted last quantifiable drug concentration will be reported.

Individual PK Parameter Rules

- Only quantifiable concentrations will be used to calculate PK parameters with the exception of special handling of certain concentrations reported below the lower limit of quantitation (BQL). Serum concentrations reported as BQL will be set to a value of zero when all of the following conditions are met:
 - The compound is non-endogenous.
 - The samples are from the initial dose period for a subject or from a subsequent dose period following a suitable wash-out period.
 - The time points occur before the first quantifiable concentration.
- All other BQL concentrations that do not meet the above criteria will be set to missing.
- Also, where two or more consecutive concentrations are BQL towards the end of a profile, the profile will be deemed to have terminated and therefore any further quantifiable concentrations will be set to missing for the calculation of the PK parameters unless it is considered to be a true characteristic of the profile of the drug.

Individual Concentration vs. Time Profiles

- Individual concentrations will be plotted utilizing actual sampling times.
- The terminal point selections will be indicated on a semi-logarithmic plot.

Average Concentration vs. Time Profiles

- The average concentration profiles will be graphed using scheduled (nominal) sampling times.

- The average concentration profiles will be graphed using arithmetic average concentrations.
- The pre-dose average concentration for single-dose data from non-endogenous compounds will be set to zero. Otherwise, only quantifiable concentrations will be used to calculate average concentrations.
- Concentrations at a sampling time exceeding the sampling time window specified in the protocol, or $\pm 10\%$, will be excluded from the average concentration profiles.
- Concentrations excluded from the mean calculation will be documented in the final study report.
- A concentration average will be plotted for a given sampling time only if 2/3 of the individual data at the time point have quantifiable measurements that are within the sampling time window specified in the protocol or $\pm 10\%$. An average concentration estimated with less than 2/3 but more than 3 data points may be displayed on the mean concentration plot if determined to be appropriate and will be documented within the final study report.

Treatment of Outliers during Pharmacokinetic Analysis

Application of this procedure to all PK analyses is not a requirement. Rather, this procedure provides justification for exclusion of data when scientifically appropriate. This procedure describes the methodology for identifying an individual value as an outlier for potential exclusion, but does not require that the value be excluded from analysis. The following methodology will not be used to exclude complete profiles from analysis.

Data within an Individual Profile

A value within an individual profile may be excluded from analysis if any of the following criteria are met:

- For PK profiles during multiple dosing, the concentration of the pre-dose sample exceeds all measured concentrations for that individual in the subsequent post-dose samples.
- For PK profiles during single dosing of non-endogenous compounds, the concentration in a pre-dose sample is quantifiable.
- For any questionable datum that does not satisfy the above criteria, the profile will be evaluated and results reported with and without the suspected datum.

Data between Individual Profiles

1. If $n < 6$, then the dataset is too small to conduct a reliable range test. Data will be analyzed with and without the atypical value, and both sets of results will be reported.

2. If $n \geq 6$, then an objective outlier test will be used to compare the atypical value to other values included in that calculation:
 - a. Transform all values in the calculation to the logarithmic domain.
 - b. Find the most extreme value from the arithmetic mean of the log transformed values and exclude that value from the dataset.
 - c. Calculate the lower and upper bounds of the range defined by the arithmetic mean $\pm 3 \times SD$ of the remaining log-transformed values.
 - d. If the extreme value is within the range of arithmetic mean $\pm 3 \times SD$, then it is not an outlier and will be retained in the dataset.
 - e. If the extreme value is outside the range of arithmetic mean $\pm 3 \times SD$, then it is an outlier and will be excluded from analysis.

If the remaining dataset contains another atypical datum suspected to be an outlier and $n \geq 6$ following the exclusion, then repeat step 2 above. This evaluation may be repeated as many times as necessary, excluding only one suspected outlier in each iteration, until all data remaining in the dataset fall within the range of arithmetic mean $\pm 3 \times SD$ of the log-transformed values.

Reporting of Excluded Values

Individual values excluded as outliers will be documented in the final report. Approval of the final report will connote approval of the exclusion.

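### At 6–7 participants per active cohort, the SAP's 3 SD outlier rule excludes valid PK values too readily, contradicts its own introduction, and requires no all-values result

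*SAP*

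**What the plan says.** SAP 9.3.1, under the heading on outliers, opens permissively. It states "Application of this procedure to all PK analyses is not a requirement", and says the method identifies a candidate for exclusion "but does not require that the value be excluded from analysis". It also limits the scope: "The following methodology will not be used to exclude complete profiles from analysis".

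The part on data between individual profiles then sets two routes.

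- **Fewer than 6 values.** The SAP regards the data as too few for a reliable range test. The instruction is: "Data will be analyzed with and without the atypical value, and both sets of results will be reported".
- **Six or more values.** Here "then an objective outlier test will be used to compare the atypical value to other values included in that calculation". Values are logged, the one furthest from the mean of all log values is set aside (step 2b), and the mean ± 3 SD of the remaining values gives the range (step 2c). If the value lies outside, step 2e says "then it is an outlier and will be excluded from analysis". The test may be repeated while at least 6 values remain.

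No definition of an atypical value is given. Exclusions are to be documented in the final report, and SAP 9.1 says "Data listings will be provided for all data that is databased". For six or more values, no analysis with every value included is required.

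SAP 9.3.2 analyses ln AUC(0-∞), the sole primary endpoint, by ANOVA with dose as a factor, and reports geometric LS means, their ratio and 90% CIs.

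**The concern.** Three things come together.

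First, the SD in the range test rests on only 5 or 6 values, after the most extreme value has been removed. It is often too small by chance, and the test looks only at the worst value of the cohort. Three such SDs are therefore a far weaker standard of evidence than three SDs in a large sample.

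Second, the introduction and step 2e differ on what follows from a flag. One says exclusion is not required; the other says it happens. Two analysts could follow the same SAP and report different primary results.

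Third, Cohorts 1 and 2 are planned with 7 randomised to active and at least 6 evaluable (Protocol 4.1.1 and 9.2), so they fall under the route for six or more values. That is the only between-profile route without dual reporting.

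If valid AUC(0-∞) values are removed this way, the residual variance is understated and the 90% CIs for the geometric LS means and their ratio are too narrow.

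**Working it through.** **Inputs from the documents.** n = 6 evaluable (SAP 7) or 7 randomised (SAP 5.2) on active per cohort. Variability: "based on an assumption of 40% coefficient of variation (CV) for between subject variability in a PK parameter of interest", so the log-scale SD is √ln(1 + 0.40²) = √ln 1.16 = 0.385. Multiplier 3, applied to the SD of the other n−1 log values (SAP 9.3.1). Two-sided 90% CIs from an ANOVA on ln AUC(0-∞) (SAP 9.3.2).

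**The plan's own figure.** SAP 7 gives about a 70% chance that the 90% CI lies within (0.7, 1.43) of the geometric mean with 6 participants. This requires 2.015 × S/√6 ≤ ln(1/0.7) = 0.357, that is S ≤ 0.434. From the chi-square distribution with 5 df, the chance is 68.1% for a log SD of 0.40 and 72.5% for 0.385. The figure reproduces. The SAP states no error rate for the outlier test.

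**Flag rate if the test is always run.** For one value, its distance from the mean of the others, divided by s√(n/(n−1)), follows a t distribution with n−2 df, where s is the SD of the others. The 3 SD limit therefore becomes t = 3/√(n/(n−1)).

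- n=6: 3/√(6/5) = 2.739 on 4 df, two-sided p = 0.0520; × 6 = 31.2%.
- n=7: 3/√(7/6) = 2.777 on 5 df, two-sided p = 0.0390; × 7 = 27.3%.

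Multiplying by n is exact here. A flagged value must account for more than half of the total sum of squares, so two cannot be flagged together:

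- n=6: 7.5/(7.5+4) × 5/6 = 54%.
- n=7: 7.714/(7.714+5) × 6/7 = 52%.

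Simulation agrees. These rates do not depend on the CV. The chance that at least one of two cohorts is flagged is 1 − (1 − 0.312)² = 53% at n=6 and 1 − (1 − 0.273)² = 47% at n=7.

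**Flag rate if only suspicious values are tested.** The SAP does not define the trigger, so I assumed a minimum fold distance and measured it in two ways: from the geometric mean of the other values, and from the geometric mean of all values (the reference used in step 2b). Clean log-normal data, 40% CV, two cohorts of equal size, pooled-variance ANOVA, single pass, every flagged value deleted. Cells show n=6 / n=7.

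| Trigger | Cohorts flagged, distance from others | Cohorts flagged, distance from all | Coverage of 90% CI for ratio, distance from others | Coverage, distance from all |
|---|---|---|---|---|
| none | 31% / 27% | same | 81.6% / 83.2% | same |
| 2-fold | 19% / 19% | 13% / 14% | 83.6% / 84.3% | about 85–86% |
| 2.5-fold | 9% / 9% | 4% / 4% | 86.5% / 86.8% | about 88% |
| 3-fold | 4% / 4% | 1% / 1% | 88.4% / 88.6% | about 90% |

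Without exclusion, coverage is 90.0%. With distance measured from the other values, the residual variance is 17–20% too low with no trigger, 15–17% with 2-fold and 5–6% with 3-fold. Repeating the test at n=7 changes coverage little (82.5% instead of 83.2% with no trigger).

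**Sensitivity to the CV.** For CV 30–50%, the 2-fold trigger flags 9–25% (from others) or 4–20% (from all). The 3-fold trigger flags 0.3–10% or 0–5%.

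**Would a stricter cut-off be enough?** Flagging 5% of clean cohorts needs 5.3 SD at n=6 and 4.7 SD at n=7. Deletion at those limits still gives about 88% coverage.

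**The case against.** The strongest reply is that the SAP never commits to running this test. A reader might take 31% or 27% as the share of cohorts that will lose a valid value. The documents do not support that: the procedure is optional and is offered as justification where exclusion is scientifically appropriate. Those figures are upper bounds. The lower figures rest on my fold triggers, and with a 3-fold trigger measured from all values the effect almost vanishes. All of this stands.

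A reader might also infer that the primary analysis is certain to be affected. That is not established either. Each participant in this single-dose study has one profile and one AUC(0-∞), so the bar on excluding complete profiles can reasonably be read as protecting it. The effect on the primary ANOVA would then be nil. The text does not settle the point, because dropping one parameter while keeping the concentrations and Cmax need not be dropping a profile.

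On the wording, the introduction can be read as governing step 2e, so the conflict may be one of drafting. It still leaves the outcome of a flag open.

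Nor are exclusions hidden: they are documented and the data are listed, so a reader could recompute the result. Protocol 9.1 plans no formal hypothesis testing, and Protocol 6.6.1 makes safety and tolerability the primary criteria for escalation. Neither depends on these CIs.

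Finally, the simulations use clean data only. They show what the rule costs when nothing is wrong, and do not measure what it gains when a value is truly aberrant.

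**Conclusion.** The point holds, with limited reach. At 6–7 values the 3 SD rule excludes too readily: it flags up to 31% or 27% of clean cohorts if always run. Under the assumed 2- to 3-fold triggers at 40% CV it flags about 4–19% (distance from the other values) or about 1–14% (distance from all values). If flagged AUC(0-∞) values are deleted, the nominal 90% CI for the ratio covers 82–83% (always run), 84–86% (2-fold) or 88–90% (3-fold). If the profile bar covers AUC(0-∞), the primary ANOVA does not change.

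Two textual faults do not depend on any simulation: step 2e disagrees with the section's introduction, and the all-values result required below 6 values is not required from 6 upward. The harm is confined to overstated precision in the primary PK description. It is worth correcting because the correction is small.

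**What to change.** In SAP 9.3.1:

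1. Keep all AUC(0-∞) values in the primary ANOVA and summary tables at every n, and state that this statistical test alone may not remove a participant's AUC(0-∞).
2. When a value is flagged, report the result without it beside the primary result as a sensitivity analysis. This extends the SAP's own approach for fewer than 6 values.
3. Reword step 2e so that it agrees with the introduction, and define in advance what makes a value atypical. The 3 SD limit can stay as the trigger for the sensitivity table. A stricter limit would trigger it less often but does not replace item 1.
4. Allow removal from the primary analysis only for a documented dosing, sampling or assay error. The 20% extrapolation text in the same section should not be cited as an exclusion rule: it only flags such values and asks for a footnote when a value is excluded.

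The cost is a few sentences, plus one sensitivity table when a value is flagged. The downside is that a truly aberrant value stays in the primary summary, with the result without it shown alongside.
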